19.5 Secondary endpoint analysis

Kaplan-Meier survival curves will be calculated for Overall Survival (OS). Participants without an OS event at the time of analysis will be censored at the time they were last known to be alive. Differences in OS between the treatment groups will be compared using multivariate

modelling (for example, an extended Cox model if appropriate) to adjust for the minimisation factors and regular aspirin use during follow-up, which will be included as a time dependent covariate, and subsequent analyses will be conducted to examine the effects of other potential effect modifiers in addition to the minimisation factors. Treatment HRs and corresponding 95% confidence intervals will be obtained from the multivariate models.

Safety analyses will summarise the AE, AR, SAE, SAR and SUSAR rates per participant, by treatment received and overall. Suspected relationship to IPE will be presented along with other causality, outcome and event duration.

QoL will be measured using the general EQ-5D and cancer specific EORTC QLQ-C30 and QLQ-LMC21 questionnaires. These will be analysed using random effects (multi-level) models to account for the hierarchical nature of repeated measures data and the models will include adjustments for baseline QoL, the minimisation factors and regular aspirin use during follow-up, which will be included as a time dependent covariate, with subsequent sensitivity analyses to adjust for any other potential effect modifiers in addition to the minimisation factors. The nature of any missing data will be investigated and if it is suspected that data are not missing at random alternative analyses will be carried out to allow for the nature of the missing data.

The number and timing of new primary cancers will be summarised descriptively by treatment group.

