7.3 Secondary Objectives

- To determine whether IPE treatment improves overall survival (OS).
- To confirm the safety and tolerability profile of IPE before and after surgery, including during chemotherapy.
- To determine whether IPE treatment improves participant reported quality of life after CRCLM surgery.
- To perform a health economic analysis of IPE treatment.
- To determine whether IPE treatment has an effect on the diagnosis of new primary cancers (excluding DCIS, cervical carcinoma *in situ*, superficial bladder carcinoma where treatment consisted of resection only and non-melanoma skin cancer where treatment consisted of resection or radiotherapy only).

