18.1 Sample size and planned recruitment rates

18.1.1 Sample size

At study outset it was specified that a sample size of 448 participants (giving 247 events) would be required to detect a HR of 0.7 for PFS in favour of EPA (the treatment arm) with a power of 80% at the 5% (2-sided) level of significance. This assumes the control arm has a median PFS of 21 months and the treatment arm has a median PFS of 30 months. It also assumed a 24 month recruitment period and a minimum 24 months follow up, and allowed for 10% dropout.

In advance of protocol version 9.0, in light of the slower than expected recruitment rate and based on the recommendation of the independent DMEC and TSC, a minimum sample size of 388 was specified. This minimum sample size takes into account a revised 67 month

recruitment period and the minimum 24 month follow-up. It was determined by considering the effect of the extended study duration and the opportunity to observe the required events in fewer patients observed for greater time. This revised minimum sample size also allows for the observed higher rate of 15% dropout related to the COVID-19 pandemic and other protocol compliance issues. All other design parameters remain unchanged, including the given number of events required to trigger analysis (247 events).

The HR for PFS in the Phase II EMT study²⁷ was 0.694, but the EPA arm, by chance, recruited a higher proportion of patients with poor prognostic features, and a multivariate analysis including these factors actually yielded a HR of 0.35 (95% confidence interval: 0.15-0.79) lending credence to the assumed more conservative HR of 0.7 chosen for this larger phase III study, given that the magnitude of benefit observed in phase II studies is often greater than that observed in the phase III counterpart.

The EMT study tested EPA-FFA 2g daily²⁷. Although the EMT2 study will evaluate IPE 4 g daily, we assume similar efficacy of EPA given as IPE, compared with EPA-FFA, for the purposes of the trial power calculation.

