The power calculation for the main secondary endpoint of OS uses a simulation approach based on an established mathematical model⁶⁰ that assumes a plateau in the time to event curves at around 4-5 years. Assuming 80% OS at 2 years in the control arm²⁸⁻²⁹, and a difference between the treatment arms of 10% in the actuarial OS rate at 2 years (equivalent to a hazard ratio of 0.47 similar to that observed in the EMT study²⁷), 448 patients (80 events) yields approximately 91% power to detect such a difference, and 78% power to detect a lesser HR of 0.55. This calculation again assumes 24 months recruitment and a minimum 24 months follow-up, a 5% (2-sided) significance level and a 10% dropout rate. Although this is an optimistic scenario, it is based on the EMT trial results²⁷, which suggested that it is entirely possible that EPA produces benefits both before and after progression, and this (secondary) endpoint encompasses that possibility. We note that OS is likely to be, if anything, slightly less than 80% at 2 years, from experience in the phase II EMT trial, which would increase the power under these assumptions.

In terms of the exploratory change in lean body mass endpoint, assuming a mean L3 skeletal muscle index score of the order of 50 cm²/m², and a standard deviation of the order of 10 in this score⁶¹ then it would be possible to detect a relatively small mean difference between the treatment arms of 5 in the L3 skeletal muscle index (e.g. from 50 to 45) with 128 patients (64 in each arm) tested at the 12-month post-surgical follow-up with 80% power and using a 5% (2-sided) significance level. Therefore, this analysis is currently restricted to participants in Leeds and Sheffield. This high power with a small sample size is possible because we are looking at differences in a continuous variable, which yields higher sensitivity to changes on smaller numbers of patients.

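### New primary cancers get only a descriptive number and timing by arm, so the objective has no effect estimate, and raw counts would tilt modestly against the longer-surviving arm

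*Protocol*

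**What the plan says.** - **Objective (Protocol 7.3).** One secondary objective is: "To determine whether IPE treatment has an effect on the diagnosis of new primary cancers", with listed exclusions. Section 17.2 repeats it as a secondary endpoint.
- **Analysis (Protocol 19.5).** The only analysis stated is: "The number and timing of new primary cancers will be summarised descriptively by treatment group". In the same section, overall survival (OS) gets an adjusted hazard ratio with 95% CI and a censoring rule, and quality of life gets adjusted random-effects models.
- **Follow-up.** Section 18.1.1 gives a revised 67-month recruitment period with at least 24 months of follow-up. Sections 13.10 and 13.11 provide record review for new primary cancers up to 84 months, for participants who consent to extended follow-up.
- **Expected survival (Protocol 18.1.1).** The OS power calculation begins: "Assuming 80% OS at 2 years in the control arm". It then posits "a difference between the treatment arms of 10% in the actuarial OS rate at 2 years", which it equates to a hazard ratio of 0.47. The protocol qualifies this: "Although this is an optimistic scenario, it is based on the EMT trial results".

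**The concern.** Two things do not fit together.

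1. **Objective and method.** The objective asks for an effect, but the method gives two separate descriptions, one per arm, with no contrast and no interval. An SAP that followed 19.5 to the letter would still not answer 7.3.
2. **Time at risk.** A new primary can be recorded only while a participant is alive and under follow-up. If IPE prolongs survival, its arm contributes more time at risk. A reader who sets the two counts side by side, over participants randomised, would then expect more cancers under IPE even if IPE has no effect on them. A real protective effect would be diluted by the same factor. The timing of the observed cases does not by itself supply a denominator.

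At stake is the reading of a secondary endpoint that bears on safety as well as benefit.

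**Working it through.** **Reproducing the protocol's own survival figures**

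- Hazard ratio implied by 90% v 80% at 2 years: ln(0.9)/ln(0.8) = 0.472, which agrees with 0.47.
- OS power with 80 events, two-sided 5%, as Φ(√80/2 × |ln HR| − 1.96): 92.2% at HR 0.47 and 76.2% at HR 0.55. The protocol states: "448 patients (80 events) yields approximately 91% power to detect such a difference, and 78% power to detect a lesser HR of 0.55". Both are within 2 points, and the protocol's own figures come from a simulation model with a plateau.

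**Time at risk by arm, with no effect on new cancers**

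Assumptions: exponential survival, equal ascertainment in both arms, administrative censoring only.

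- Control death hazard: h = −ln(0.8)/2 = 0.1116 per year. IPE death hazard: h × HR.
- Mean time alive over follow-up T: (1 − e^(−hT))/h. At T = 2 years and HR 0.47 this is 1.793 years (placebo) and 1.899 years (IPE), a ratio of 1.06.
- For staggered entry, this is averaged over uniform follow-up. With 67 months' recruitment and analysis at 67 + 24 = 91 months, follow-up runs from 24 to 91 months, capped at 84. That gives 3.61 v 4.16 years at HR 0.47, a ratio of 1.15.

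| Follow-up | HR 0.47 | HR 0.55 | HR 0.70 |
|---|---|---|---|
| 2 years each | 1.06 | 1.05 | 1.03 |
| 2 to 4 years | 1.09 | 1.08 | 1.05 |
| 24 to 91 months, capped at 50 | 1.11 | 1.10 | 1.06 |
| 24 to 91 months, capped at 84 | 1.15 | 1.13 | 1.08 |
| 7 years each (upper bound) | 1.21 | 1.17 | 1.11 |

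With the survival curves flat after 4.5 years, the 1.15 at HR 0.47 becomes 1.145.

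**In cases**

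The protocol gives no rate of new primary cancers, so rates (λ) of 0.5%, 1% and 2% per year are assumed. Expected first new primaries per arm are n × λ × (mean time free of both death and new cancer). At HR 0.47:

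| Assumed rate | 194 per arm, 2–7 years (placebo v IPE) | Excess | 224 per arm, 2–4 years (placebo v IPE) | Excess |
|---|---|---|---|---|
| 0.5% | 3.3 v 3.8 | 0.5 | 2.8 v 3.1 | 0.3 |
| 1% | 6.6 v 7.5 | 0.9 | 5.6 v 6.1 | 0.5 |
| 2% | 12.9 v 14.7 | 1.8 | 11.0 v 12.0 | 1.0 |

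Here 194 = 388/2 and 224 = 448/2. With follow-up of 2 to 7.6 years, the 194-per-arm excess at 2% is 2.0.

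In 4,000 simulated trials at 1% per year, 194 per arm, 2–7 years and HR 0.47, IPE showed more cases in 54%, fewer in 35% and a tie in 10%. With no survival effect the split was about 44/44/12.

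**Which summary removes the tilt**

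- Rate per person-year, or cause-specific hazard: ratio 1.00 by construction, because the new-cancer hazard was set equal.
- Cumulative incidence with death as a competing event, λ/(λ+h) × (1 − e^(−(λ+h)T)), at λ = 1% and HR 0.47: 1.78% v 1.88% at 2 years (1.06), 3.17% v 3.54% at 4 years (1.12), 4.71% v 5.67% at 7 years (1.20). This is almost the same tilt as the raw counts.

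**The case against.** The strongest case against has four parts.

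- **It is SAP detail.** Section 19.1 promises a full SAP, and 19.5 does not exclude person-time or incidence curves. This stands for the choice of denominator alone. It does not cover the mismatch between an objective about an effect and a method fixed as descriptive, since both are in the protocol.
- **Timing is included.** The plan is number and timing, not bare counts, and nothing says the denominator is participants randomised. This stands: the tilt arises only if raw counts are compared.
- **Few events make description reasonable.** With about 14 events in total, the 95% interval around a hazard ratio of 1 is exp(±1.96 × 2/√14), or 0.35 to 2.85, which swamps a ratio of 1.15. This stands as a reason to label the estimate as estimation only. It is not a reason to omit it, because the interval tells the reader how little the data can settle.
- **The larger ratios use favourable inputs.** HR 0.47 is called optimistic in 18.1.1, the final analysis in 19.3 may be triggered earlier by events, and extended follow-up needs separate consent. Each of these shrinks the tilt.

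A reader might infer that IPE will look carcinogenic if it prolongs survival. The documents do not support that. Under the 1% scenario above, IPE shows fewer or equal cases in about 45% of trials. A crude Fisher test, which the protocol does not plan, would flag a nominally significant IPE excess in 1.8% of trials, against 1.2% with no survival effect.

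**Conclusion.** The point holds at low severity. As written, 19.5 gives no effect estimate for an objective that asks about an effect. It also names no time at risk in a trial with unequal follow-up.

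If raw counts are compared, the tilt against the longer-surviving arm is about 6–15% at OS HR 0.47 and 3–8% at HR 0.70. The 7-year-for-all case (21% and 11%) is only an upper bound. In cases, the excess at HR 0.47 is roughly 0.5 to 2 over the longer follow-up and 0.3 to 1.0 over 2–4 years.

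These figures rest on exponential survival, no effect of IPE on new cancers, equal ascertainment, no dropout, and assumed new-primary rates of 0.5–2% per year that are not in the protocol. Dropout or refusal of extended follow-up would shorten follow-up and reduce the tilt.

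**What to change.** In Protocol 19.5, keep the number and timing by arm and add:

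- the rate of first new primary cancer (with the stated exclusions) per person-year by arm, with person-time running from randomisation to first new primary, death or last assessment;
- a cause-specific hazard ratio with 95% CI, labelled as estimation only because few events are expected.

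Cumulative incidence with death as a competing event may be added as a supporting display, with a note that it does not correct for longer survival in one arm.

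The cost is wording. The sources are already planned: assessment for new primaries at visits 3 to 10 and at record review, and notification of deaths. The downside is a hazard ratio with a wide interval that may be over-read unless the label is kept.

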19.6 Subgroup Analyses

A subgroup analysis comparing the outcomes for patients that receive ≥ 2 weeks of IMP prior surgery and patients that receive < 2 weeks of EPA will be performed. Further subgroup analyses will be performed to investigate the effect of aspirin and EPA and the effect of EPA on the MSI status of the primary colorectal cancer on PFS.

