10.4.2 Treatment Allocation

Participants will be randomised on a 1:1 basis to receive either IPE 4 g daily or placebo and will be allocated a trial number and a unique kit-code to identify which box of capsules (active [IPE] or placebo) will be dispensed. The participant's randomisation allocation will not be disclosed in order to maintain the blinding of the trial.

A computer-generated minimisation programme that incorporates a random element will be used to ensure that treatment groups are well balanced for the following participant characteristics, details of which will be required for randomisation:

- 'Downsizing' chemotherapy prior to liver resection* (yes or no)
- Known extrahepatic CRC metastases with curative treatment planned (yes or no)
- Current regular (intention to use daily) aspirin use:

- yes to current regular aspirin use
- no to current regular aspirin use
- Add-aspirin trial participant still taking IMP (placebo or aspirin, double-blind trial so treatment allocation not required to be known at EMT2 randomisation)
- Randomising Centre
- Time between randomisation date and date of planned liver resection surgery (<2 weeks or ≥2 weeks)

*For definition see Section 9.4

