10.4.3 Registration and Randomisation Process

Registration and randomisation will be performed centrally using the CTRU automated 24-hour telephone/web randomisation service. Authorisation codes and PINs, provided by the CTRU, will be required to access the randomisation system. Only authorised members of staff at the trial sites will be able to access the randomisation system.

Participants will be registered into the trial and issued a trial number. Women of childbearing potential will be required to take a pregnancy test prior to randomisation. Participants who are not women of childbearing potential may proceed directly to randomisation during the same telephone call/web session.

The following information will be required in order for the participant to be registered and randomised. The person performing the registration/randomisation should have all details to hand:

- Name and code (assigned by the CTRU) of trial site
- Name of person performing the registration/randomisation
- Patient initials, and date of birth
- Confirmation of eligibility
- Confirmation of whether the participant is a woman of childbearing potential
- Confirmation of written informed consent
- Stratification factors (see section 0)
- Planned operation date

**Direct line for 24-hour registration/randomisation
[name]**

**Website for registration/randomisation:
<https://lictr.leeds.ac.uk/webrand/>**

Please ensure that the Eligibility Checklist and Randomisation CRFs have been completed before starting the registration/randomisation process

At the end of the registration process a unique EMT2 trial participant identifier will be assigned. At the end of the randomisation process a unique kit-code will be provided which identifies the box of capsules that needs to be dispensed by pharmacy. The participant's randomisation allocation will not be disclosed in order to maintain the blinding of the trial.

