12.2 Treatment Regimen

Participants will be randomised to receive either 4 x 1g capsules of IPE or 4 identical placebo capsules daily. Participants should take their capsules with food.

The trial treatment should be taken daily from the date of randomisation until the participant has completed study treatment (maximum of four years treatment post liver resection).

Trial treatment will continue following diagnosis of disease progression or diagnosis of a new primary cancer as there is still potential for EPA treatment to improve outcomes of any new or recurrent cancer.

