12.2.1 Treatment breaks

While it is preferred that participants continue their trial medication daily, it may be necessary for participants to take one or more treatment breaks during follow-up. Examples of possible reasons for a treatment break include in-patient hospital stays (eg. for CRCLM surgery) if nil by mouth is specified or during chemotherapy treatment or other concurrent treatment that results in a persistent adverse reaction (AR) or difficulty taking IMP.

In the event of a persistent AR, a dose reduction (see Section 12.2.4) should be tried prior to a treatment break. Details of any dose reduction or break in treatment should be recorded on the Treatment CRF, including the duration and reason.

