13.22 End of follow up phase and End of Trial

The end of the intervention and follow-up phases of the trial is defined as the date when the last participant recruited has reached 2 years post-surgery or randomisation (if that individual

was randomised but didn't undergo surgery). The end of the EMT2 trial will occur at the date of the collection of the last participant's last data item.

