19.4 Primary endpoint analysis

The primary endpoint is progression free survival (PFS) (see section 17 for definition).

PFS will be analysed using the 95% confidence interval of the hazard ratio; the 95% confidence interval of the difference in median PFS will also be presented to aid interpretation. Kaplan-Meier survival curves will be calculated for PFS. Patients without a PFS event at the time of analysis will be censored at the time they were last known to be alive and progression-free. Differences in PFS between the treatment groups will be compared using multivariate modelling (for example, an extended Cox model if appropriate) to adjust for the minimisation factors of 'downsizing' chemotherapy, extrahepatic CRC metastases, randomising centre, and time between randomisation and surgery and also regular aspirin use during follow-up which will be included as a time dependent covariate. A sensitivity analysis will also be conducted to examine the effects of other potential effect modifiers in addition to the minimisation factors. The primary analysis will be the multivariate analysis which adjusts for the minimisation factors and regular aspirin use during follow-up. Treatment HRs and corresponding 95% confidence intervals will be obtained from the multivariate models.

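### Section 19.6 defines the pre-surgery exposure subgroup by treatment received after randomisation and, as worded, compares exposure groups instead of IPE with placebo, although a baseline factor with the same two-week cut is already recorded

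*Protocol*

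**What the plan says.** Protocol section 19.6 describes its first subgroup analysis as "comparing the outcomes for patients that receive ≥ 2 weeks of IMP prior surgery and patients that receive < 2 weeks of EPA". It gives no further definition of the groups, and for this subgroup it names neither an endpoint nor a contrast between the randomised arms.

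Other sections bear on this:

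- Section 10.4.2 lists, among the minimisation factors, "Time between randomisation date and date of planned liver resection surgery (<2 weeks or ≥2 weeks". The stated purpose is balance: "A computer-generated minimisation programme that incorporates a random element will be used to ensure that treatment groups are well balanced".
- Section 10.4.3 lists "Planned operation date" among the items needed before a participant can be randomised.
- Section 19.4 adjusts the primary model for "randomising centre, and time between randomisation and surgery and also regular aspirin use during follow-up".
- Section 12.2 sets the intended exposure: "The trial treatment should be taken daily from the date of randomisation until the participant has completed study treatment". Section 12.2.1 accepts that "it may be necessary for participants to take one or more treatment breaks during follow-up", and section 12.2.4 allows a permanent stop after persistent adverse events.
- Section 13.22 provides for a participant who "was randomised but didn't undergo surgery".
- Section 19.2 puts every analysis except safety and tolerability on an intention-to-treat basis.
- Section 17.1 starts PFS at randomisation, while sections 13.5 and 13.6 time the scheduled visits and CT scans from surgery. Section 13.4 expects surgery within 6 weeks of randomisation.

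**The concern.** The wording has three faults.

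1. **The grouping variable arises after randomisation.** How much IMP is taken before surgery depends on whether the operation happens when planned and on whether the participant pauses or stops. If stopping differs between arms, even an IPE-versus-placebo comparison inside such groups loses the protection of randomisation. Participants who are never operated on cannot be classified.
2. **The contrast is between exposure groups.** Longer-exposed patients are set against shorter-exposed patients. The section does not say that IPE is compared with placebo within each group.
3. **The two sides do not match.** Section 11 classes both IPE and placebo as IMP, whereas EPA is the active treatment. Read literally, a mixed-arm group is compared with an active-arm group, and placebo participants with under two weeks of treatment belong to neither.

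The question is whether pre-operative loading matters. A non-randomised contrast could give a false positive or a false negative answer to it. The different time origins of PFS and the scan schedule push in one direction, in favour of the longer wait.

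**Working it through.** **Reference figure.** Section 19.6 states no number. The protocol's event target is reproduced because it sets the information available to any subgroup analysis. By Schoenfeld's formula with HR 0.7, 80% power and 5% two-sided (section 18.1.1):

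events = 4 × (1.960 + 0.842)² / (ln 0.7)² = 4 × 7.849 / 0.1272 ≈ 247, which matches the protocol.

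**Timing artefact.** For progression found on a scheduled scan, PFS = wait from randomisation to surgery + time from surgery to that scan. Suppose there is no drug effect and the second term does not depend on the wait. PFS then lengthens by exactly the wait.

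- The documents give no distribution of waits. Assume that treatment lasts for the whole wait, and that waits are uniform over 0 to 2 weeks in one group and 2 to 6 weeks in the other.
- Group means are 1 and 4 weeks, a difference of 3 weeks = 21 / 30.4 ≈ 0.7 months.
- Against the assumed control median of 21 months (section 18.1.1): 0.69 / 21 ≈ 3%.
- Upper limit between two individuals, one operated on almost at once and one at 6 weeks: 42 / 30.4 ≈ 1.4 months, or 1.38 / 21 ≈ 6.6%.

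Deaths and progression dated by clinical assessment (sections 13.12 and 17.1) do not follow the scan timetable and are not shifted. Within a stratum of planned time to surgery the artefact is expected to cancel between IPE and placebo. It does not cancel between exposure groups.

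**Selection, direction only.** An illustrative simulation with no treatment effect assumed planned waits uniform over 3 to 42 days, a frailty that raises both the PFS hazard and early stopping, and somewhat more early stopping among frail IPE patients. It did not model the scan timetable.

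| Comparison | Event-rate ratio (true value 1) |
|---|---|
| Exposure received, ≥2 vs <2 weeks | 0.93 |
| Same, literal IMP vs EPA wording | 0.92 |
| IPE vs placebo within received-exposure groups (≥2; <2 weeks) | 0.98; 1.02 |
| Planned time, ≥2 vs <2 weeks | 1.00 |
| IPE vs placebo within planned-time groups | 1.00; 1.00 |

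All inputs are assumptions, so only the direction is informative.

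**Power of the replacement analysis.** For a treatment-by-stratum interaction with D1 and D2 events, SE of the log ratio of hazard ratios = √(4/D1 + 4/D2), and power = Φ(|ln 0.7| / SE − 1.96) for a ratio of 0.7. The documents do not give the split, so a range is shown with D1 + D2 = 247.

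| Share of events in larger stratum | SE | Power, ratio 0.7 | Ratio detectable with 80% power |
|---|---|---|---|
| 50% | 0.255 | 29% | 0.49 |
| 70% | 0.278 | 25% | 0.46 |
| 80% | 0.318 | 20% | 0.41 |
| 90% | 0.424 | 13% | 0.31 |

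**The case against.** The strongest reply is that section 19.6 is a short summary. Under a heading on subgroups, and with the intention-to-treat rule of section 19.2, it could be read as IPE versus placebo within each group, with the detail left to the SAP promised in section 19.1. The protocol also uses EPA loosely for the intervention elsewhere. That reading could restore the randomised contrast, and the absence of an interaction test alone would be no finding. It does not rescue the grouping. The section says what patients receive, so the groups would still form after randomisation and would still be undefined without surgery. A SAP that follows the text inherits this, and one that does not will depart from the protocol.

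A second reply is that actual exposure has a rationale, since section 6.2 reports tissue incorporation approaching steady state at two weeks. This stands, and it supports keeping the exposure analysis as a supplement.

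A third is that early stopping for intolerance may be rare: section 6.2.1 reports only two symptom-related withdrawals in the phase II trial. This also stands. It weakens tolerance as a driver but leaves surgical delay and breaks.

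A reader might also infer more than the documents support:

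- That randomisation was carried out by planned time to surgery. Planned time is one of several factors in a minimisation programme with a random element.
- That patients who wait longer differ in fitness or disease extent. This is plausible, but no section documents it.
- That the aspirin subgroup has the same defect. Section 19.6 does not say that it uses post-baseline aspirin; the time-dependent aspirin covariate belongs to the models in sections 19.4, 19.5 and 19.7.

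**Conclusion.** The point holds for the subgroup definition and for the contrast as worded. Following section 19.6 literally gives a non-randomised comparison on a post-randomisation variable, with mismatched sides, while a baseline variable with the same cut is required for every randomised participant.

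The timing artefact averages about 3 weeks (0.7 months, roughly 3% of the 21-month control median) for scan-dated events. This assumes uniform waits within each group, treatment throughout the wait, and a time from surgery to detection that does not depend on the wait. The 1.4 months is a maximum between two individuals and should not be read as the bias between groups. The effect of selection cannot be sized from the documents.

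The consequence is moderate. The primary PFS analysis, the 247-event target and the sample size are unaffected. The replacement analysis has low power and can only be exploratory.

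**What to change.** Rewrite the first sentence of section 19.6 along these lines: the IPE-versus-placebo hazard ratio for PFS, with its 95% confidence interval, will be estimated within the minimisation strata of planned time from randomisation to surgery (<2 weeks, ≥2 weeks), with a treatment-by-stratum interaction test; this analysis is exploratory.

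If an analysis by treatment actually received is kept, use IMP on both sides, state how participants without surgery are handled, and label it supplementary and non-randomised. No change to the aspirin subgroup is needed on this ground.

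The cost is wording only. The stratum is recorded at randomisation, so no new data are needed and neither the sample size nor trial conduct changes.
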